## **9 ASSESSMENT OF SAFETY**

### **9.1 Specification of Safety Parameters**

As the safety profile of azithromycin is well established, and this trial is not powered to detect new, unknown safety signals, there will be no azithromycin-related Adverse Event (AE) collection or Serious Adverse Events (SAEs) reporting during this study only solicited adverse events will be collected.

Additionally, a blood draw is minimum risk since there is no more risk than the normal standard of care.

The collection of the nasopharyngeal swabs is minimum risk with some discomfort possibly experienced by the subject; in some cases, it may cause mild bleeding. This risk is no greater than encountered during the collection of such swabs for routine clinical care.

### **9.2 Methods and Timing for Assessing, Recording, and Analyzing Safety Parameters**

#### **9.2.1 Adverse Events**

Adverse Event (AE): International Council on Harmonisation (ICH) E6 defines an AE as any untoward medical occurrence in a patient or clinical investigation subject administered a pharmaceutical product regardless of its causal relationship to the study treatment. FDA defines an AE as any untoward medical occurrence associated with the use of a drug in humans, whether or not considered drug related. An AE can therefore be any unfavorable and unintended sign (including an abnormal laboratory finding), symptom, or disease temporally associated with the use of a medicinal (investigational) product.

#### **9.2.2 Solicited Adverse Events**

Solicited adverse events are common and known to occur following administration of the study product. Solicited adverse events will be recorded according to the study timeline. Solicited adverse events will be used to determine DOOR assignment as summarized in Table 3, Section 3.

#### **9.2.3 UADE Definition**

An unanticipated adverse device effect (UADE) per 21 CFR 812.3(s): is defined as any serious adverse effect on health or safety or any life-threatening problem or death caused by, or associated with a device if that effect, problem, or death was not previously identified in nature, severity, or degree of incidence in the investigational plan or application (including a

supplementary plan or application), or any other unanticipated serious problem associated with a device that relates to the rights, safety, or welfare of subjects.

## **9.3 Reporting Procedures**

### **9.3.1 Reporting UADEs Using SAE Forms**

Unanticipated adverse device effect (UADE) are unexpected and will be reported appropriately should any occur. Any UADE must be entered into AdvantageEDCSM (within 24 hours of site awareness) and reported to the IRB. Please see the protocol-specific MOP for details regarding this procedure.

### **9.3.2 Reporting for Studies Conducted Under DMID Sponsorship**

Any UADEs will be collected from the first study enrollment through study completion. The Site Investigator is responsible for documenting and reporting all UADEs that are reported during the study, regardless of their relationship to study procedures.

Information to be collected includes a record of any concomitant medication, event description, time of onset, clinician's assessment of severity and relationship to study procedures/study device. All UADEs will be followed to adequate resolution or stabilization. Resolution of an UADE is defined as the return to pre-enrollment status or stabilization of the condition with the expectation that it will remain chronic. Time of resolution/stabilization of the event will be collected for device procedure related UADEs.

DMID will evaluate each report of a UADE in accordance with 21CFR812.46(b). DMID will notify the FDA, all participating site principal investigators (i.e., all principal investigators to whom the sponsor is providing study device), and all reviewing IRBs through the participating sites' principal investigators. Notification will occur as soon as possible but in no case later than 10 working days after the sponsor is notified of the UADE. Relevant follow up information to a safety report will be provided as soon as the information is available.

### **9.3.3. Reporting of Pregnancy**

The only active treatment in this study is azithromycin, which is a pregnancy Class B drug. It is used as a standard treatment in pregnant women. As such, pregnancy will neither be screened for nor reported but may be collected per medical history.

## **9.4 Type and Duration of the Follow-up of Subjects After Adverse Events**

Study related solicited events and UADEs will be followed until resolved or considered stable.

## 9.5 Halting Rules

### 9.5.1 Study Halting Rules

Subject safety data will be reviewed on an ongoing basis. If any of the following events occur while a subject is on study, then enrollment will be stopped, and data will be reviewed. A decision to proceed or to terminate the trial will be made in consultation with the DSMB (including the independent safety monitor), NIH/NIAID/DMID, and the clinical investigators.

Further study enrollment will be halted for DSMB review/recommendation if any of the following are reported:

- Hospitalization of 5 subjects (or  $\geq 5\%$  if more than 100 subjects randomized) that requires intensive care due to persistent/worsening LRTI within 28 days of initiation of study treatment
- More than 10 subjects ( $\geq 10\%$  if more than 100 subjects randomized) require hospitalization for persistent/worsening LRTI within 3 days of initiation of study treatment
- More than 20 subjects ( $\geq 20\%$  if more than 100 subjects randomized) require the administration of non-study directed systemic antibiotic therapy for persistent/worsening LRTI within 3 days of initiation of study treatment
- Any subject experiences death (that is not the result of trauma or accident) prior to Visit 4 (Day 11+3 days) **and** that is suspected to be related to study treatment (or participation).

### 9.5.2 Individual Halting Rules (Termination of Study Product Administration)

Study product administration may be discontinued if any of the following criteria are met:

- Any clinical adverse event (AE), intercurrent illness, or other medical condition occurs that, in the opinion of the investigator, continued receipt of study product would not be in the best interest of the subject;
- New onset of illness or condition that meets exclusion criteria, at the investigator's discretion
- Inadequate clinical response that requires off-study antimicrobial therapy.
  - Subjects who require off-study antimicrobial therapy will be defined as having an inadequate clinical response.

Subjects may stop study drug treatment at any time of their own volition or at the advice of their treating provider or the study investigators. Subjects who stop study product for any reason will be regarded as having withdrawn from treatment but not as having withdrawn from the study (i.e, subjects will be asked to continue to participate in follow-up visits). All subjects with an inadequate clinical response will be referred to a non-study healthcare provider for evaluation and possible treatment outside of the clinical study. If requested, unblinding can occur if clinically indicated as determined by the treating clinician and the study's site investigator.

At the time of withdrawal, subjects will undergo an early termination visit if they are not willing to participate in the remaining follow-up visits.

## 9.6 Safety Oversight

### 9.6.1 Data and Safety Monitoring Board (DSMB)

Safety oversight will be conducted by a DSMB that is an independent group of experts that monitors subject safety and advises DMID. The DSMB members will be separate and independent of study personnel participating in this trial and should not have scientific, financial or other conflict of interest related to the study. The DSMB will consist of members with appropriate expertise to contribute to the interpretation of the data from this trial.

The DSMB will review study progress and subject, clinical and safety data at the following time points:

- Annually at the completion of each respiratory disease season;
- Final review meeting, approximately 6-8 months after clinical database lock to review the cumulative unblinded safety and efficacy data for this trial. The data will be provided in a standard summary format;
- Ad hoc when a halting rule is met, for immediate concerns regarding observations during the study, or as needed.

The DSMB will operate under the rules of a DMID-approved charter that will be written at the organizational meeting of the DSMB. At this time, each data element that the DSMB needs to assess will be clearly defined. Procedures for DSMB reviews/meetings will be defined in the charter. The DSMB will review applicable data to include, but not limited to, study progress and subject, clinical, and safety data that may include enrollment and demographic information, medical history, concomitant medications, physical examination, dosing, and solicited events. Additional data may be requested by the DSMB, and interim statistical reports may be generated as deemed necessary and appropriate by DMID. The DSMB may receive data in aggregate and presented by group. The DSMB will meet and review this data at scheduled time points or ad hoc as needed during the study as defined in the DSMB charter. As an outcome of each review/meeting, the DSMB will make a recommendation as to the advisability of proceeding with study product administration, and to continue, modify, or terminate the study.

DMID, the PI, or the DSMB chair may convene the DSMB on an ad hoc basis according to protocol criteria or if there are immediate concerns regarding observations during the course of the study. The DMID Medical Monitor is empowered to stop enrollment and study treatment if the halting criteria is met or in case of any safety concern.

## **10 CLINICAL MONITORING**

### **10.1 Site Monitoring Plan**

Site monitoring is conducted to ensure that the human subject protections, study and laboratory procedures, study intervention administration, and data collection processes are of high quality and meet sponsor, ICH/GCP guidelines and applicable regulations, and that the study is conducted in accordance with the protocol, protocol-specific MOP and applicable sponsor standard operating procedures. DMID, the sponsoring agency, or its designee will conduct site-monitoring visits as detailed in the clinical monitoring plan.

Site visits will be made at standard intervals as defined by DMID in a separate monitoring plan and may be made more frequently as directed by DMID. Monitoring visits will include, but are not limited to, review of regulatory files, accountability records, eCRFs, informed consent forms, medical and laboratory reports, and protocol and GCP compliance. Site monitors will have access to the study site, study personnel, and all study documentation according to the DMID-approved site monitoring plan. Study monitors will meet with site principal investigators to discuss visit findings.

## 11 STATISTICAL CONSIDERATIONS

### 11.1 Study Hypothesis

The primary hypothesis is that placebo therapy is non-inferior in efficacy to azithromycin treatment in terms of clinical improvement rates when administered to adults with suspect lower respiratory tract infection (LRTI) and a procalcitonin level of  $\leq 0.25$  ng/mL. The primary time point of interest is 4 days after administration of study product (i.e. Day 5).

Null hypothesis:  $\pi_{\text{placebo}} - \pi_{\text{azithromycin}} \leq -12.5\%$ ,

Alternative hypothesis (non-inferiority):  $\pi_{\text{placebo}} - \pi_{\text{azithromycin}} > -12.5\%$ ,

where  $\pi$  represents the probability of clinical improvement at study Day 5. 12.5% is the non-inferiority margin used for this study.

### 11.2 Sample Size Considerations:

The study will be powered to the primary endpoint of clinical improvement with 560 participants included in the according-to-protocol analysis population at Day 5. To achieve this sample size, approximately 674 enrolled subjects will need to be randomized (1:1) to placebo or azithromycin treatment to have 80% power to rule out a 12.5% increase in the clinical improvement rate with antibiotic therapy compared to placebo assuming a clinical improvement rate of 57.6% in each group using a two-sided 95% confidence interval with continuity correction, in a per-protocol analysis (i.e., allowing for 16.9% loss in each treatment group to follow up/rescue medication).

The primary analysis will include an intention-to-treat (ITT) estimation of the difference in proportions of subjects with clinical improvement at Day 5 in the antibiotic and placebo groups with a two-sided 95% confidence interval.

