5. SAMPLE SIZE CONSIDERATIONS

The null hypothesis corresponding to the primary analysis if this study is:

Null hypothesis: $\pi_{\text{placebo}} - \pi_{\text{azithromycin}} \leq -12.5\%$,

Alternative hypothesis (non-inferiority): $\pi_{\text{placebo}} - \pi_{\text{azithromycin}} > -12.5\%$,

where π represents the probability of clinical improvement at study day 5. 12.5% is the non-inferiority margin used for this study.

The study was first designed assuming that 840 subjects would have to be enrolled in order to randomize 420 (50%) subjects and have 80% power to rule out a 12.5% increase in the clinical improvement rate with antibiotic therapy compared to placebo assuming a clinical improvement rate of 80% in each group using a two-sided 95% confidence interval (CI) using normal approximation with continuity correction with continuity correction, in the according-to-protocol analysis population at D5V (ATP-5) as defined in Section 6.3 (i.e., allowing for 15% loss in each treatment group).

These assumptions underlying the original target sample size of 420 subjects were assessed by a planned, interim, blinded analysis after approximately 210 subjects completed or terminated from the study. The interim report was finalized on January 9th, 2020. The observed clinical improvement rate at the time of the interim analysis was 57.6% in each group which is lower than the initially assumed 80% rate. Due to this finding, new sample size estimates have been generated to account for actual observed rates of clinical improvement and protocol deviations that preclude inclusion in the primary analysis. The total sample size was increased to enroll 674 subjects which will allow 560 subjects eligible for the ATP-5 analysis population allowing for 16.9% loss in each treatment group to follow up/rescue medication. This new sample provides 80% power to rule out a 12.5% increase in the clinical improvement rate with antibiotic therapy compared to placebo assuming a clinical improvement rate of 57.6% in each group using a two-sided 95% CI with continuity correction, in an according-to-protocol analysis (i.e., allowing for 16.9% loss in each treatment group to follow up/rescue medication).

Although analysis using an ATP population was used for determination of sample size (to account for missing data), the primary analysis will be an ITT analysis using all randomized subjects.

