6.6. Interim Analyses and Data Monitoring

There will be no interim analysis of efficacy or futility. An interim analysis was performed to assess the assumptions used for sample size calculations including rate of adequate clinical improvement, rate of evaluable subjects, and the frequency of enrolled subjects with PCT ≤ 0.25 ng/mL.

Assumptions underlying the original target sample size of 420 subjects were assessed by a planned, interim, blinded analysis after 213 subjects completed or terminated from the study. The original assumptions were that the overall rate of clinical improvement at Visit 3 would be 80% and that there would be no more than 15% unevaluable subjects (i.e. withdraw, fail to complete D5V or didn't meet other inclusion criteria for the according-to-protocol population at Day 5). In this interim analysis, the required sample size needed for 80% power to rule out a 12.5% increase in the clinical improvement rate with antibiotic therapy compared to placebo was computed using the observed overall rate of clinical improvement across both treatment groups and the observed proportion of subjects eligible for an according-to-protocol analysis at D5V. The findings of the interim analysis concluded that 674 subjects needed to be randomized to achieve an ATP-5 sample size of 560 (280 per arm) to achieve 80% power using clinical improvement rate of 57.6% in each group allowing for 16.9% loss in each treatment group. The protocol was updated to reflect the updated sample size.

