8. EFFICACY EVALUATION

All efficacy variables will be listed by subject. Data will be summarized by treatment group. Continuous efficacy variables will be summarized with the number of observations, mean, median, standard deviation, minimum, and maximum. Categorical efficacy variables will be summarized by number and percent in each category.

All statistical tests are performed at the $\alpha=0.05$ significance level. The primary hypothesis is a one-sided test but uses a two-sided 95% CI to make a conclusion about non-inferiority.

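### The step from the printed assumptions to 560 evaluable subjects does not reproduce: 280 per arm give about 83% power, not 80%, a discrepancy on the conservative side

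*Protocol*

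**What the plan says.** Protocol section 11.1 fixes the margin: "12.5% is the non-inferiority margin used for this study". Section 11.2 sizes the trial on 560 subjects in the ATP-5 population, "assuming a clinical improvement rate of 57.6% in each group using a two-sided 95% confidence interval with continuity correction", and allows 16.9% loss in each arm. On the number to randomise it says: "To achieve this sample size, approximately 674 enrolled subjects will need to be randomized (1:1) to placebo or azithromycin treatment to have 80% power". The power claim is "80% power to rule out a 12.5% increase in the clinical improvement rate with antibiotic therapy compared to placebo".

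The SAP agrees. Section 5 says: "This new sample provides 80% power to rule out a 12.5% increase in the clinical improvement rate". Section 6.6 reports the outcome of the blinded interim re-estimation: "674 subjects needed to be randomized to achieve an ATP-5 sample size of 560 (280 per arm) to achieve 80% power". On the error rate, SAP section 8 says: "The primary hypothesis is a one-sided test but uses a two-sided 95% CI to make a conclusion about non-inferiority". That is one-sided 0.025.

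SAP section 5 also describes the design before re-estimation: 420 randomised, 80% improvement in each arm, 15% loss, 80% power, with the interval named as a normal approximation with continuity correction. Neither document gives a formula, the software or a rounding rule for either calculation. SAP section 5 adds that the ATP population served for sizing only and that the primary analysis is ITT.

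**The concern.** The interim re-estimation exists to deliver one set of figures: how many evaluable subjects, how many randomised, and at what power. All the inputs are printed, so a reader should be able to recover 560 from them. The usual formula gives a smaller number for 80% power, or a higher power for 560. Either the plan understates its power or something that went into the calculation is not printed. What is at stake is whether the figure that sets recruitment can be traced, not the validity of the analysis.

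**Working it through.** **Inputs.** Rate p = 0.576 in both arms, so the true difference is zero (Protocol 11.2). Margin d = 0.125 (Protocol 11.1). One-sided 0.025, z = 1.96 (SAP 8). Power 80%, z = 0.8416. Evaluable n = 280 per arm (SAP 6.6). Loss 16.9% (Protocol 11.2).

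**1. Loss step, as the plan has it.** 560 / (1 − 0.169) = 673.9, so 674. This reproduces.

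**2. Check of the method on the earlier design** (80% in each arm, 15% loss).
- Uncorrected: n = (1.96 + 0.8416)² × 2 × 0.8 × 0.2 / 0.125² = 160.7 per arm.
- Continuity-corrected, using n/4 × [1 + √(1 + 4/(n·d))]²: 176.4, so 177 per arm and 354 evaluable.
- Randomised: 354 / 0.85 = 416.5, so 417 against the stated 420.
- Conversely, 420 × 0.85 = 357 evaluable gives 80.5% power. The method fits.

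**3. The same method on the revised inputs.**
- Uncorrected: n = (1.96 + 0.8416)² × 2 × 0.576 × 0.424 / 0.125² = 245.4 per arm.
- Continuity-corrected: 245.4/4 × [1 + √(1 + 4/(245.4 × 0.125))]² = 261.1, so 262 per arm and 524 evaluable.
- The stated 560 is 36 higher. 524 is 6.4% below it.

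**4. Power at the stated 280 per arm.** The correction widens the interval by ½(1/280 + 1/280) = 1/280 = 0.00357.
- Standard error: √(2 × 0.576 × 0.424 / 280) = 0.04177.
- Power: Φ((0.125 − 0.00357)/0.04177 − 1.96) = Φ(0.947) = 82.8%.

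**5. Whether another method explains 280 per arm.**

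| Method | Power at 280 per arm | Evaluable N for 80% |
|---|---|---|
| Standard continuity correction | 82.8% | 524 |
| No correction | 84.9% | 492 |
| Hauck-Anderson | 83.9% | 508 |
| Fleiss pooled, corrected (0.576 vs 0.451) | 82.2% | 532 |
| Standard correction at p = 0.5 (largest variance) | 82.0% | 534 |
| Exact enumeration, corrected Wald | 83.2% | – |
| Exact enumeration, corrected Newcombe | 83.8% | – |
| Doubled correction (1/n₁ + 1/n₂) | 80.6% | 554 |

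Only the doubled correction comes close. On the earlier design it gives 76.7% power at 357 evaluable and would need 452 randomised against the stated 420. None of these methods fits both designs.

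**The case against.** **At least 80%.** The best defence is that 80% is a design target which 560 meets, and that section 11.2 calls 674 approximate. Read as a minimum, the power statements in Protocol 11.2 and SAP 5 are not false. But Protocol 11.3.2 says the interim analysis computed the sample size required for 80% power, and SAP 6.6 says 674 were needed. That is the language of a computed requirement. The earlier design was rounded up by 3 randomised subjects (417 to 420). Here the gap is 36 evaluable subjects, and neither document mentions a cushion.

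**An unspecified correction.** The documents do not define the continuity correction, and the interim report that produced the figure is not available here. A doubled correction could lie behind 560. It would then have replaced the method that fits the earlier design, and the plan would need to say so. This part of the objection stands: a different correction, input or rounding rule is possible and should be printed if it exists.

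**Stronger readings that the documents do not support.**
- A reader might infer that recruitment should drop to 524 / 0.831 = 631 randomised, 43 fewer than 674. That would change the design after the re-estimation, and nothing in the discrepancy calls for it.
- Solving backwards for 280 per arm at 80% gives a margin of about 12.1%, so a reader might suspect that the margin changed. Every statement of the hypothesis and of the power prints 12.5%.
- The primary interval comes from linear regression without a continuity correction, so a reader might take the uncorrected 84.9% as the power of the primary analysis. That figure is for 280 observed subjects per arm. The primary analysis is ITT with multiple imputation and a visit-day covariate, and its power has not been computed.

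**Conclusion.** The point holds as a discrepancy between the printed inputs and the printed result. Power is understated by about 3 percentage points. The discrepancy is conservative: the trial is not underpowered, and no estimate, confidence interval, error rate or non-inferiority decision depends on it.

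The conclusion assumes that both arms truly improve at 57.6%, that the normal approximation named for the earlier design carries over to the revised one, and that the correction is the standard one. The first assumption is not critical, because even the largest possible variance leaves the requirement at 534. The third matters most: with a doubled correction the revised figure nearly fits, but the earlier one does not. The 82.8% describes the ATP-5 sizing calculation only.

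**What to change.** Keep 560 evaluable and 674 randomised. In Protocol 11.2 and SAP sections 5 and 6.6, use the same sentence, for example: with 280 evaluable subjects per arm in ATP-5, 57.6% improvement in each arm and a 12.5-point margin, a two-sided 95% normal-approximation interval with continuity correction gives about 83% power.

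If a different correction, an additional input or deliberate rounding led to 280 per arm, print that instead, with the formula or software, so that the figure can be recovered.

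Do not lower the recruitment target, and do not quote 85% as the power of the ITT multiple-imputation analysis. The cost is wording in three places, with no additional patients and no change to the analysis.

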## 3.2 Study Outcome Measures

### 3.2.1 Primary Outcome Measures:

The efficacy of azithromycin versus placebo on Day 5 will be based on clinical improvement.

- Clinical improvement will be defined as fulfillment of **all** the following criteria:
  1. Improvement in at least two symptoms present at enrollment (i.e., cough, sputum production, chest pain, or difficulty breathing) or one symptom and at least one vital sign abnormality present at enrollment. For symptoms, at least a one-step improvement (e.g., improvement from moderate to mild cough) will be considered a clinical improvement (Table 1). For vital sign abnormalities, normalization of the

presenting abnormal vital sign will be considered a clinical improvement. Qualifying vital signs and their normal values will include the following:

- temperature (<37.8°C or 100.0°F),
  - pulse (<90 bpm),
  - respiratory rate (≤20 breaths per minute),
2. Absence of deterioration in any qualifying symptom (i.e., cough, sputum production, chest pain, or difficulty breathing); or new vital sign abnormality not present at enrollment. For symptoms, at least a one-step deterioration (e.g. worsening from mild to moderate cough) will be considered clinical deterioration (Table 1).
  3. Absence of fever in the day preceding or at the Day 5 Visit (fever is defined as ≥37.8 °C or 100.0 °F, measured anywhere on the body).
  4. No medically attended visit to an ambulatory medical facility (e.g., ED, outpatient clinic, urgent care center) or hospitalization for persistent or worsening LRTI at any time after randomization (persistent or worsening LRTI is defined as receipt of a non-study antibiotic [parenteral or oral] treatment for LRTI or its complication).  
**Note:** receipt of a non-study antibiotic after study Day 5 will not be regarded as satisfying this definition if it is related to a new non-respiratory process that is unrelated to the prior diagnosis of LRTI

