## **11.4 Final Analysis Plan**

The intention-to-treat (ITT) analysis population will consist of all randomized subjects. According-to-protocol (ATP) analysis populations will consist of subjects with no major protocol deviations regarding inclusion/exclusion criteria that consumed 5 doses of study product by Visit 3. The first dose of study drug should be taken within 24 hours of randomization. Subjects who miss a scheduled dose but resume the recommended dosing schedule within 24 hours remain eligible for ATP. However, in order for a subject to be eligible for the ATP-5 analysis, Visit 3 should be performed on or after the last day of study drug consumption while remaining within the 5+3 window. The ATP-5 analysis population will have the further restriction that the subjects must have completed an in-person Visit 3 within the protocol-defined time window. The ATP-11 analysis population will consist of the ATP analysis population with the further restriction that the subjects must have completed Visit 4 within the protocol-defined time window. The ATP-28

analysis population will consist of the ATP analysis population with the further restriction that the subjects must have completed Visit 5 within the protocol-defined time window.

Unless otherwise stated, all hypothesis tests and confidence intervals will be two-sided with  $\alpha=0.05$ . Statistical tests and confidence intervals will not correct for multiplicity.

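### Rescue antibiotics are labelled as loss in the sample-size text but count as failure in the endpoint, and the five-dose ATP rule can remove known failures from the supportive analyses

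*Protocol*

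**What the plan says.** Protocol 11.2 plans 674 randomized subjects to give 560 in ATP-5, "in a per-protocol analysis (i.e., allowing for 16.9% loss in each treatment group to follow up/rescue medication". SAP 5 has the same label: "allowing for 16.9% loss in each treatment group to follow up/rescue medication". Neither document says how the 16.9% divides between loss to follow-up and rescue. Protocol 5 and 11.3.2 also describe the unevaluable subjects, and neither names rescue.

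The endpoint treats the event differently. Criterion 4 in Protocol 3.2.1 requires that there was no medically attended visit or hospitalization for persistent or worsening LRTI, and adds that "persistent or worsening LRTI is defined as receipt of a non-study antibiotic [parenteral or oral] treatment for LRTI or its complication". Protocol 9.5.2 says of the halting rule: "Subjects who require off-study antimicrobial therapy will be defined as having an inadequate clinical response".

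Protocol 11.4 limits the ATP sets to subjects without major eligibility deviations "that consumed 5 doses of study product by Visit 3". The exclusion list in SAP 6.3 covers eligibility deviations, dose count, timing of the first dose, resumption after a missed dose, visit completion and window, and insufficient data. Rescue is not on it.

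Need for off-study antimicrobial therapy is an individual halting criterion. Stopping study product is optional in Protocol 9.5.2 but stated as certain in 5.4.3 and 6.3.

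**The concern.** One event is given two roles. In the sample-size text it takes a subject out of the evaluable set; in the endpoint it settles the outcome as not improved. The five-dose rule gives the first role practical effect. A subject who has a criterion 4 event on Day 3 and stops study product cannot reach five doses and leaves all three ATP sets. A subject with the same event who takes all five doses and attends in window stays in as a failure. Inclusion thus depends on whether dosing continued after rescue.

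Two uses of the ATP sets are exposed. SAP 6.5 uses them, without imputation, to examine the robustness of the primary result. Protocol 11.4.2 (items 4 to 7) and SAP 8.2.5 and 8.2.6 analyse antibiotic days, return visits, ED visits and hospitalizations through Days 11 and 28 in ATP-11 and ATP-28 only. There, the excluded subjects carry some of the events being counted.

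**Working it through.** **Inputs from the documents.** Improvement rate: "assuming a clinical improvement rate of 57.6% in each group" (Protocol 11.2). Margin: "12.5% is the non-inferiority margin used for this study" (Protocol 11.1). Target: "80% power to rule out a 12.5% increase in the clinical improvement rate with antibiotic therapy compared to placebo" (Protocol 11.2). Size: 674 randomized, 337 per arm, 560 in ATP-5. Loss: 16.9%.

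**Input assumed.** The rate of rescue before dose 5 in each arm, because no document gives it.

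**1. The plan's own figure.** 560 / (1 - 0.169) = 673.9, so 674. Power at 280 per arm is Φ[(0.125 - c/n) / √(2 × 0.576 × 0.424 / n) - 1.96]. This gives 82.8% with a continuity correction of 1/n (c = 1) and 80.6% with 2/n (c = 2). The stated size is reproduced and is not short.

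**2. Effect of dropping rescued failures.** If a fraction r of an arm is rescued early, all of them failures, and is excluded, the retained improvement rate is p / (1 - r). Put the true difference at the margin: 57.6% on azithromycin, 45.1% on placebo. The chance of a lower bound above -12.5% should then be 2.5%.

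Take 12% other exclusions at random, and rescue of 3% on azithromycin and 6% on placebo:

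- Azithromycin: 0.576 / 0.97 = 0.5938, n = 337 × 0.88 × 0.97 = 287.7.
- Placebo: 0.451 / 0.94 = 0.4798, n = 337 × 0.88 × 0.94 = 278.8.
- Difference: -11.4 points.
- Standard error: √(0.5938 × 0.4062 / 287.7 + 0.4798 × 0.5202 / 278.8) = 0.0416.
- Chance of a lower bound above -12.5%: Φ[(-0.1140 + 0.125) / 0.0416 - 1.96] = 4.5%.
- Pooled loss: 1 - (287.7 + 278.8) / 674 = 16.0%, or 12 + 4.5 = 16.5% if the exclusions are added. Both are within 16.9%.

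**3. Other assumed rescue rates.** Same truth, 337 per arm, no other exclusions:

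| Rescue, azithromycin / placebo | ATP difference (points) | Chance of lower bound above -12.5% |
|---|---|---|
| 5% / 5% | -13.2 | 1.7% |
| 10% / 10% | -13.9 | 1.0% |
| 2% / 5% | -11.3 | 4.9% |
| 5% / 10% | -10.5 | 7.2% |

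**4. Break-even.** Bias at the margin is zero when 0.576 / (1 - rA) - 0.451 / (1 - rP) = 0.125. For rA = 5%, rP = 1 - 0.451 / (0.6063 - 0.125) = 6.3%. For rA = 10%, rP = 1 - 0.451 / (0.64 - 0.125) = 12.4%. The ratio is about 1.25 in both cases. With 57.6% in both arms and equal rescue, the two retained rates are equal and there is no bias.

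**5. Effect of keeping rescued subjects as failures.** Randomize the same 674, with no true difference and rescue equal in the arms:

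| Share of the 16.9% that is rescue | n per arm | Improvement rate | Power (1/n; 2/n) |
|---|---|---|---|
| None | 280 | 57.6% | 82.8%; 80.6% |
| Half | 308.5 | 0.576 × 0.831 / 0.9155 = 52.3% | 85.7%; 83.8% |
| All | 337 | 0.576 × 0.831 = 47.9% | 88.7%; 87.2% |

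The required number does not rise.

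**The case against.** The ATP rule has no rescue criterion. Exclusion is indirect, and rescued subjects with five doses and an in-window visit are already counted as failures. This stands, and it limits the point to rescue before dose 5.

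The direction is not fixed: equal rescue moves a true deficit away from non-inferiority. This also stands. Excess rescue on placebo is, however, what one would expect if withholding azithromycin did harm, so the check is weakest in the situation it should detect.

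Not every rescued subject is a known failure. Criterion 4 and its derivation in SAP 6.5.1.4 need a medically attended visit or hospitalization together with an LRTI antibiotic. The inadequate response in Protocol 9.5.2 belongs to the halting rule, not the endpoint. This stands, and the fix is confined to documented criterion 4 events.

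A reader might infer that the trial's type I error is inflated. The documents do not support that. SAP 8.1.1 lets the primary ITT analysis alone decide non-inferiority, and ITT comprises all randomized subjects. The SAP 8.4.1 pseudo-code merges imputed subjects with ATP-5 data without saying how observed outcomes outside ATP-5 enter. That is a separate ambiguity; SAP 6.3.1 imputes only missing values.

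A reader might also quote larger effects, such as 14% at rescue of 4% versus 12%. With 12% other exclusions, that case implies a pooled loss of 19% to 20%, and 3% versus 9% implies 17% to 18%. Both exceed the stated 16.9%.

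**Conclusion.** The point holds in a limited form. The loss label in Protocol 11.2 and SAP 5 conflicts with criterion 4, and the five-dose rule removes some known failures from ATP-5, ATP-11 and ATP-28. The supportive analyses can lean toward non-inferiority if early rescue is about 1.25 times as frequent on placebo, or more, with the true difference at the margin. In the illustration that fits the stated loss, the shift is 1.1 points (-12.5 to -11.4) and the chance of a favourable lower bound is 4.5% rather than 2.5%; a larger placebo excess gives more. These figures rest on assumed rescue rates, on every excluded rescued subject being a failure, and on other exclusions being random. The decisive ITT analysis and the stated power are not affected by the ATP rule. The change is worth making because it is cheap and the ATP sets serve as a robustness check.

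**What to change.** 1. In Protocol 11.4 and SAP 6.3 and 6.3.2, state that an otherwise ATP-eligible subject who took fewer than five doses because of a documented criterion 4 event (medically attended visit or hospitalization with a non-study antibiotic for LRTI) on or before the visit stays in the ATP sets as not improved. The SAP 6.3 exclusion for dosing not resumed after a missed dose needs the same exception.
2. Report the ATP result without these subjects as a sensitivity analysis, because inclusion then depends on outcome.
3. In Protocol 11.2 and SAP 5, remove rescue medication from the loss label, or state its share of the 16.9%.
4. Reconcile Protocol 9.5.2 with 5.4.3 and 6.3 on whether stopping study product is optional or certain, since this governs how many subjects are affected.

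The cost is a few sentences, a change to the population flag and one extra set of ATP results. No more patients or data are needed. ATP improvement rates will fall by an amount that depends on the unstated rescue share: from 57.6% to 52.3% if half of the 16.9% is rescue, and to 47.9% in the extreme case that all of it is.
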